10.3. General Statistical Considerations

The statistical analyses will be performed using R, version 4.1.2 or higher. Any statistical tests of hypotheses will employ a level of significance of alpha=0.05.

11. SAMPLE SIZE JUSTIFICATION

Assuming a pooled standard deviation of 36.8^5 seconds and a mean difference of 0 seconds, the study would require a sample size of: 32 for each group (i.e. 64 eyes of 32

subjects), to achieve a power of 80% and a level of significance of 5%, for declaring that the Active Sentry is not inferior to the Ozil at 23 seconds margin of non-inferiority. To account for drop outs a total of 35 subjects (70 eyes) will be recruited.

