7. SUBJECTS

7.1. *Subject Population*

Eligible test subjects will be 50 years of age or older and who are eligible to undergo sequential bilateral uncomplicated cataract surgery.

A total of 70 eyes of 35 subjects at one site will be enrolled. Both eyes of a subject must be enrolled. Subjects must meet the inclusion criteria. Prior to enrollment, subjects will be provided information on the study and asked to sign a patient information and consent form to participate. The patient information and consent form will be approved by an appropriate ethics committee.

7.2. *Inclusion Criteria*

Subjects are eligible for the study if they meet the following criteria:

Note: Ocular criteria must be met in both eyes.

- Be eligible to undergo sequential bilateral uncomplicated cataract surgery.
- Undergo uneventful cataract surgery.
- Gender: Males and Females.
- Both eyes must have same grade of cataract.
- Willing and able to provide written informed consent for participation in the study.
- Willing and able to comply with scheduled visits and other study procedures.

7.3. *Exclusion Criteria*

If any of the following exclusion criteria are applicable to the subject or either eye, the subject should not be enrolled in the study.

- Patient under 50 years of age.

- Unable to complete sequential bilateral cataract surgery in both eyes by the same surgeon (JS).
- Patient cataract surgery complicated by posterior capsular tear.
- Any disease state deemed by PI that increases risk of complicated cataract surgery (ie Pseudoexfoliation syndrome, zonular dehiscence, history of eye trauma, RA, prior refractive surgery, etc).

The principal investigator reserves the right to declare a patient ineligible or non-evaluable based on medical evidence that indicates they are unsuitable for the trial.

Pregnancy has a known effect on the stability of refractions and visual acuity. As such, subjects who become pregnant during the study will not be discontinued but their data may be excluded from analyses of effectiveness.

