8. STUDY DESIGN

8.1. Study Design

This study is a single site, single-masked, randomized, prospective, contralateral eye study of the efficiency of the Active Sentry handpiece at low IOP compared with the Ozil at high IOP. Subjects will be assessed pre-operatively, operatively and at 1 day and 1 week post-operatively. Clinical evaluations will include measurement of visual acuity and central corneal thickness (CCT).

The primary outcome measure will be the total aspiration time between groups on day of surgery.

Secondary outcome measures are as follows:

- Total fluid volume between groups on day of surgery.
- Total phaco time between groups on day of surgery.
- Total case time between groups on day of surgery.
- Aspiration time during phaco between groups on day of surgery.
- Central corneal thickness (CCT) between groups at postoperative day 1 and week 1.

Exploratory outcome measures are as follows:

- Cumulative dissipated energy between groups on day of surgery.

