10. ANALYSIS PLAN

10.1. Analysis Data Sets

All subjects who are enrolled in the study will be evaluated for safety. Efficacy analyses will be performed based on data from those eyes where uncomplicated cataract surgery was completed.

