10.2. Statistical Methodology

A summary of the data will be prepared for all measurement time points.

For variables measured on a continuous scale, these summaries will include the sample size, as well as the mean, standard deviation, median, minimum, and maximum. For variables measured on a categorical scale, summaries will provide the number and percentage of subjects in each category. These summaries will be provided for all eyes completing the study.

The difference in the aspiration time between groups will be used to test the non-inferiority hypothesis. If the upper boundary of the 95th confidence interval is not greater than 23, non-inferiority will be claimed. In the event that non-inferiority is demonstrated, then a test of superiority will be performed.

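### Section 11's 80% power is not tied to section 10.2's decision rule: 32 per group comes from one-sided 5% without pairing, but the rule is a 95% interval in a contralateral design

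*Combined protocol and SAP*

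**What the plan says.** Section 8.1 describes a "single site, single-masked, randomized, prospective, contralateral eye study of the efficiency of the Active Sentry handpiece", so each subject supplies one eye to each handpiece. Section 7.2 adds "Both eyes must have same grade of cataract".

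Section 10.2 compares aspiration time between groups and gives the success rule: "If the upper boundary of the 95th confidence interval is not greater than 23, non-inferiority will be claimed". It then adds "In the event that non-inferiority is demonstrated, then a test of superiority will be performed". It names no test, does not say whether the interval is one- or two-sided, and does not say that it is for a within-subject difference.

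Section 10.3 sets the error rate: "Any statistical tests of hypotheses will employ a level of significance of alpha=0.05". No side is given.

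Section 11 derives 32 per group (64 eyes of 32 subjects), "Assuming a pooled standard deviation of 36.8^5 seconds and a mean difference of 0 seconds", with a 23 s margin, "to achieve a power of 80% and a level of significance of 5%, for declaring that the Active Sentry is not inferior". It recruits 35 subjects to allow for dropouts. It gives no between-eye correlation and no SD of the within-subject difference. The raised 5 after 36.8 is a citation mark.

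**The concern.** A power statement means something only for a named decision rule. Section 11's number comes from a 5% one-sided test of two groups treated as independent. Section 10.2's rule, as most readers would take an unqualified 95% interval, is a 2.5% one-sided test, and the design calls for a paired comparison. So the 80% may describe a test other than the one that decides the trial.

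This is the only hypothesis that the trial is powered for. The side of the interval sets the chance of a false non-inferiority claim at a true difference of 23 s (5% or 2.5%) and the largest observed difference that still passes. The superiority test that follows also has no stated side.

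**Working it through.** **Inputs.** SD 36.8 s, true difference 0, margin 23 s, power 80%, alpha 5% (side not stated), 32 per group and 35 recruited, all from section 11. The 95% interval is from section 10.2. The between-eye correlation ρ is not in the documents and is varied as an assumption.

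**1. Reproducing 32.** For two independent groups, normal approximation, n per group = 2 × (z₁₋α + z₀.₈)² × SD² / margin².
- One-sided 5%: 2 × (1.645 + 0.842)² × 36.8² / 23² = 31.65, so 32. This is the plan's figure. Pairs with ρ = 0 give the same result.
- One-sided 2.5%: 2 × (1.960 + 0.842)² × 36.8² / 23² = 40.19, so 41.
- If 36.8 s were the SD of the paired difference, the normal formula gives 15.83 (16 pairs) at one-sided 5% and 20.09 (21 pairs) at one-sided 2.5%. Neither is 32.

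**2. Unpaired power under each reading.** At 32 per group the standard error is 36.8 × √(2/32) = 9.2 s, and 23/9.2 = 2.5.
- One-sided 95% bound: Φ(2.5 − 1.645) = 80.4%; noncentral t (62 df) 79.6%.
- Two-sided 95% interval: Φ(2.5 − 1.960) = 70.5%; noncentral t 69.2%.
- At 35 per group (normal / t): 83.4% / 82.7% for the one-sided bound and 74.4% / 73.2% for the two-sided interval.

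**3. Paired power.** With 36.8 s as the per-eye SD (assumption), the SD of the difference is 36.8 × √(2(1 − ρ)): 52.0, 45.1 and 36.8 s at ρ = 0, 0.25 and 0.5. Noncentral t with n − 1 df gives:

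| Rule | Pairs | ρ = 0 | ρ = 0.25 | ρ = 0.5 |
|---|---|---|---|---|
| Two-sided 95% interval | 32 | 67.8% | 79.9% | 92.8% |
| Two-sided 95% interval | 35 | 71.9% | 83.5% | 94.9% |
| One-sided 95% bound | 32 | 78.8% | 88.1% | 96.5% |
| One-sided 95% bound | 35 | 82.0% | 90.5% | 97.6% |

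**4. What 80% requires with the paired two-sided interval.** The SD of the difference must be at most 44.99 s with 32 complete pairs (ρ ≈ 0.25) or 47.18 s with 35 (ρ ≈ 0.18). For the one-sided bound the limits are 51.17 s and 53.62 s.

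**5. Where the two readings part.** The largest observed difference that passes is 23 − t × SE.
- 32 per group, unpaired: 23 − 1.999 × 9.2 = 4.6 s (two-sided interval) and 23 − 1.670 × 9.2 = 7.6 s (one-sided bound).
- 35 pairs at ρ = 0.25: 7.5 s and 10.1 s.
- Every result that passes the two-sided rule also passes the one-sided rule. The chance of opposite conclusions is therefore the difference between the table's rows. With 35 pairs and a true difference of 0 it is 10%, 7% and 3% at ρ = 0, 0.25 and 0.5.

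**The case against.** The best defence is that nothing was miscalculated. The figure of 32 reproduces, and if section 10.2 means a one-sided 95% bound, sections 10.2, 10.3 and 11 agree on 5% one-sided and 80%. That stands. It shows how the number was probably obtained, but it does not fix the decision rule. The number is not conclusive either: a paired calculation at one-sided 2.5% gives 40.19 × (1 − ρ), which also rounds up to 32 for ρ of about 0.20 to 0.23.

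The second defence is that pairing restores the power. Both eyes have the same cataract grade and one surgeon operates on both, so some positive correlation is plausible. This largely stands. The unpaired figure of about 70% is near the bottom of the range, and if 36.8 s were the SD of the within-subject difference, 32 pairs would give about 93% even with the two-sided interval. But section 11 takes no credit for pairing, and section 10.2 does not commit to a paired analysis.

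A reader might infer that the trial is underpowered. The documents do not support that: they give no correlation, and modest pairing or a one-sided bound brings power back to 80%. A reader might also infer that the side would be picked once results are known. Nothing suggests this, and the data analyzer is masked, although masking does not itself settle the side.

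The three extra subjects do not settle the matter. Section 11 assigns them to dropouts. Section 10.1 also defines the efficacy set by eye ("Efficacy analyses will be performed based on data from those eyes where uncomplicated cataract surgery was completed"), so a subject with one excluded eye would contribute no complete pair.

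**Conclusion.** The point holds as a mismatch between the stated power and the stated rule. It is not an arithmetic error or a proven shortfall. With section 10.2 read as an ordinary two-sided 95% interval, section 11's inputs support about 70% at 32 per group unpaired (69.2% by t, 70.5% by normal), not 80%. A paired t analysis of the same rule runs from 68% to 93% with 32 pairs, and from 72% to 95% with 35, as the correlation goes from 0 to 0.5.

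These paired figures assume that 36.8 s is a per-eye SD. The word pooled favours this, but it cannot be checked: the figure carries citation 5 and the reference list has three entries. If a one-sided 95% bound was intended, the 80% stands by the normal formula, and the remaining defect is that the rule does not say so.

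**What to change.** Make three wording changes before the data are analysed.

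- **Section 10.2.** State: *Non-inferiority will be claimed if the two-sided 95% confidence interval (paired t) for the mean within-subject difference in total aspiration time, Active Sentry minus Ozil, has an upper limit of 23 seconds or less.*
- **Section 10.3.** State the matching one-sided 0.025 for non-inferiority, and the side of the superiority test.
- **Section 11.** Restate power for this paired rule, with the assumed SD of the within-subject difference and its source. Power of 80% needs an SD of at most about 45 s with 32 complete pairs, or 47 s with 35.

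If the sponsor intended a one-sided 95% bound, say so in all three sections and state the 5% one-sided error openly. Power should still be restated for the paired analysis: by paired t, 32 pairs give 78.8% at zero correlation, and 80% needs an SD of the difference of at most about 51 s.

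The cost is text only; no extra subjects are required. The downside of the two-sided rule is that the stated power becomes conditional on an assumption, and is 68% to 72% if the two eyes are uncorrelated.

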13. QUALITY COMPLAINTS AND ADVERSE EVENTS

All subjects will be monitored for adverse events over the course of the study. A place to record any adverse event is included on each case report form.

13.1. General Information

An Adverse Event (AE) is any untoward medical occurrence in a subject who is administered a study treatment regardless of whether or not the event has a causal relationship with the treatment. An AE, therefore, can be any unfavorable or unintended sign (including an abnormal laboratory finding), symptom, or disease temporally associated with the study treatment, whether or not related to the treatment. In clinical studies, an AE can include an untoward medical occurrence occurring at any time, including run-in or washout periods, even if no study treatment has been administered.

13.2. Monitoring for Adverse Events

At each visit, after the subject has had the opportunity to spontaneously mention any problems, the Investigator should inquire about AEs by asking if the patient has any problems.

13.3. Procedures for Recording and Reporting AEs and SAEs

Subsequent to signing an informed consent form, all untoward medical occurrences that occur during the course of the study must be documented on an Adverse Event Form (AEF). A separate AEF must be filled out for each event. When possible, signs and symptoms indicating a common underlying pathology should be documented as one comprehensive event. For each recorded event, the AE documentation must include the onset date, outcome, resolution date (if event is resolved), intensity (i.e., severity), any action with study treatment taken as a result of the event, and an assessment of the adverse event's relationship to the study treatment.

Nonserious Adverse Events

A nonserious AE is defined as any untoward change in a subject's medical health that does not meet serious criteria noted below (e.g., is not life-threatening, does not require hospitalization, does not prolong a current hospitalization, is not disabling, etc.). All adverse events must be reported regardless of whether or not they are related to the study treatment.

For nonserious adverse events, an AEF containing all available information will be collected on a routine basis and submitted to the Medical Monitor at the close of the study.

Serious Adverse Events

A serious adverse event (SAE) is defined as any adverse experience that meets any of the following criteria:

- Results in death.
- Is life-threatening.

NOTE: Life-threatening means that the subject was at immediate risk of death from the reaction as it occurred; i.e., it does not include a reaction which hypothetically might have caused death had it occurred in a more severe form.

- Requires inpatient hospitalization or prolongation of existing hospitalization.
NOTE: In general, hospitalization signifies that the individual remained at the hospital or emergency ward for observation and/or treatment (usually involving an overnight stay) that would not have been appropriate in the physician's office or an out-patient setting. Complications that occur during hospitalization are AEs. If a complication prolongs hospitalization or fulfills any other serious criteria, the event is serious. When in doubt as to whether "hospitalization" occurred, the event should be considered serious.
- Results in persistent or significant disability/incapacity. Disability is defined as a substantial disruption of a person's ability to conduct normal life functions.
NOTE: The term disability means a substantial disruption of a person's ability to conduct normal life functions. This definition is not intended to include experiences of relatively minor medical significance such as uncomplicated headache, nausea, vomiting, diarrhea, influenza, or accidental trauma (e.g., sprained ankle) which may interfere or prevent everyday life functions but do not constitute a substantial disruption.

- Is an important medical event. An important medical event is an event that may not result in death, be life-threatening, or require hospitalization but may be considered an SAE when, based upon appropriate medical judgment, it may jeopardize the subject and may require medical or surgical intervention to prevent one of the outcomes listed in the definitions for SAEs. Examples of such medical events include allergic bronchospasm requiring intensive treatment in an emergency room or at home, blood dyscrasias or convulsions that do not result in subject hospitalization, or the development of drug dependency or drug abuse.

All available information on a serious adverse event(s) and any other associated AE, if applicable, must be forwarded to the study coordinator for forwarding to the Medical Monitor immediately (i.e., within one working day of the Investigator's or site's knowledge of the event) as follows:

- In studies utilizing EDC (electronic data capture), all available information for the SAE and any associated AE(s) must be entered immediately into the EDC system.
- Additional information for any applicable event is to be reported as soon as it becomes available.

In addition to the reporting of serious adverse events to the study Medical Monitor, the SAE must be reported to the IRB / IEC according to their requirements.

The investigator must document all adverse device events (serious and nonserious but related) and all serious adverse events (related and unrelated) on the Adverse Device Effect and Serious Adverse Event Form. Any device quality complaints will also be documented.

- Both the Quality Complaint Form and the Adverse Device Effect and Serious Adverse Event Form must be e-mailed immediately to the study coordinator ([name]).**
- Additional relevant information is to be reported as soon as it becomes available.**

Study coordinator contact information is provided below.

**Table 13.3.-1:
Contact Information for Study**

Study Staff	Business Phone	e-mail	24-hour Office Phone

12.3.1 Intensity and Causality Assessments

For every adverse event and quality complaint, the investigator must assess the causality as Related or Not Related to the medical device under investigation. An assessment of causality will also be performed by the Medical Monitor utilizing the same definitions, as shown below:

Causality

Related	An adverse event or quality complaint classified as related may be either definitely related or possibly related where a direct cause and effect relationship with the medical device has not been demonstrated, but there is a reasonable possibility that the adverse event or quality complaint was caused by the medical device.
Not Related	An adverse event or quality complaint classified as not related may either be definitely unrelated or simply unlikely to be related (i.e., there are other more likely causes for the adverse event or quality complaint).

Where appropriate, the investigator must assess the intensity (severity) of the adverse event as mild, moderate, or severe based on medical judgment with consideration of any subjective symptom(s), as defined below:

Intensity (Severity)

Mild	An adverse event is mild if the subject is aware of but can easily tolerate the sign or symptom.
Moderate	An adverse event is moderate if the sign or symptom results in discomfort significant enough to cause interference with the subject's usual activities.
Severe	An adverse event is severe if the sign or symptom is incapacitating and results in the subject's inability to work or engage in their usual activities.

The investigator must document any action taken (i.e., medication, intervention, or treatment plan) and outcome of the adverse event or quality complaint when applicable.

13.4. Follow-Up of Adverse Events and Quality Complaints

The investigator is responsible for adequate and safe medical care of subjects during the study and for ensuring that appropriate medical care and relevant follow-up procedures

are maintained after the study. Any additional data from these follow-up procedures must be documented and available to the study coordinator who, with the Medical Monitor, will determine when the data need to be documented on the CRFs.

13.5. Safety Analyses

The type, severity, duration and frequency of reported ocular adverse events will be tabulated. Adverse events will also be summarized for events that were considered treatment-related.

14. GCP, ICH and ETHICAL CONSIDERATIONS

This study will be conducted in compliance with Good Clinical Practices (GCPs), including International Harmonization (ICH) Guidelines, and in general, consistent with the 1996 version of the Declaration of Helsinki. In addition, all applicable local, state and federal requirements will be adhered to.

This study is to be conducted in accordance with Institutional Review Board regulations. The investigator will obtain appropriate IRB/ethics committee approval prior to initiating the study. The study will be registered with clinicaltrials.gov.

15. STANDARD EVALUATION PROCEDURES

Table 15.1. Proposed Visits and Study Assessments

Activity	Both Eyes	First Eye			Second Eye		
	Pre-operative	Operative	Post-operative	Post-operative	Operative	Post-operative	Post-operative
	Visit 1	Visit 2	Visit 3	Visit 4	Visit 2a	Visit 3a	Visit 4a
			Day 1	Week 1		Day 1	Week 1
Informed Consent	X						
Demographics	X						
General Information: Medical History	X						
Surgery		X			X		
Total Phaco Time		X			X		
Total Aspiration Time		X			X		
Total Fluid Volume		X			X		
Total Case Time		X			X		
Cumulative Dissipated Energy (CDE)		X			X		
Central Corneal Thickness (CCT)	X		X	X		X	X
Slit Lamp Examination	X		X	X		X	X
Monocular uncorrected distance VA	X		X	X		X	X
Monitor for Adverse Events and Device Deficiencies		X	X	X	X	X	X
Complete Exit Form ¹							X

¹ Complete Exit Form upon termination of subject participation, or at Visit 7, whichever occurs first.

17. FINANCIAL AND INSURANCE INFORMATION/STUDY RELATED INJURIES

Every effort to prevent study-related injury will be taken by the Study Doctor and staff. In the event a patient is injured as a direct result of the study while following the Study Doctor's instructions and the study requirements, the patient will be instructed to contact his or her doctor immediately. The Study Doctor is to treat the injured subject as needed

for those injuries caused directly by this research study. In the event of injury or illness caused by or occurring during a subject's participation in this research study, all charges for medical care provided to the subject will be billed to his or her insurance company. The Study Doctor or Sponsor does not offer to cover the medical care costs for injuries or illnesses that are not caused directly by the research study. The Sponsor does not offer to provide any other compensation, unless specifically agreed to elsewhere in this document. This information will be provided to each study subject before the start of the study in the consent form.

